### 13.7 Version 4.0 (China-specific Amendment)

- Section 1 (Synopsis) and 3.3.2 (Exploratory Endpoints): [REDACTED]
- Table 3 (Randomized Controlled Period Schedule of Study Assessments for the AChR-Ab+ Population), Table 4 (Randomized Controlled Period Schedule of Study Assessments for the MuSK-Ab+ Population), and Table 5 (Open-label Period Procedures for AChR-Ab+ and MuSK-Ab+ Populations): [REDACTED]  
[REDACTED] (Tables 3 and 4 only) were removed from the tables, as these samples will not be collected in China. Footnotes were updated accordingly.
- Section 5.1 (Inclusion Criterion #1), Section 6.1.2 (Randomized Controlled Period), Table 3, and Table 4: Japan-specific procedures were removed from the China-specific protocol.

- Section 10.5 (Biological Specimens and Data): Reference to future use of biological samples was removed because that will not be performed in China.

### 13.8 Version 3.0

- Section 1 (Synopsis) and Section 3.1.2 (Primary Endpoint): “MG-ADL profile score” was changed to “MG-ADL score” to reflect the more commonly used name for the outcome.
- Section 2.1.4 (Risk Assessment for Inebilizumab): The summary of inebilizumab use during pregnancy was updated.
- Section 5.2 (Exclusion Criteria): Exclusion Criterion #11 was updated to change the CD19+ B-cell threshold for inclusion from one-half the lower limit of normal to  $\geq 40$  cells/ $\mu$ L for consistency with other exclusion criteria.
- Section 5.2 (Exclusion Criteria): Exclusion Criterion #27 was added to exclude subjects unable to read since subjects are required to read and complete PROs during the study.
- Section 5.2 (Exclusion Criteria): Exclusion Criterion #28 was added to exclude subjects with untreated active or latent TB. Section 6.1.1 (Screening Period), Table 2: QuantiFERON®-TB Gold blood test was added to the table of screening procedures. Section 6.2.7 (Clinical Laboratory Assessments): QuantiFERON®-TB Gold test was added to the list of laboratory assessments.
- Section 6.1.1 (Screening Period): Measurement of AChR and MuSK titers was removed from the Screening Visit since only serostatus will be determined.
- Section 6.1.1 (Screening Period), Section 6.1.2 (Randomized Controlled Period): The statements that patient questionnaires should be performed before other procedures were removed to allow sites to have more flexibility in the order of procedures.
- Section 6.1.2 (Randomized Controlled Period) and Tables 3 and 4: A requirement was added for Japanese sites to call study subjects every 2 weeks during the RCP to evaluate their clinical status. This was added at the request of the Japan Pharmaceuticals and Medical Devices Agency.
- Section 6.1.2 (Randomized Controlled Period), Tables 3 and 4 and Section 6.1.3 (Open-label Period), Table 5: It was clarified at which visits MGFA clinical classification and MGFA [REDACTED] procedures are to be performed.
- Section 6.1.2 (Randomized Controlled Period), Table 4: The order of procedures was changed to make it consistent with Table 3.
- Section 6.1.3 (Open-label Period): In the text and Table 5 it was clarified which procedures do and do not need to be repeated at OLP Day 1 if the visit is done within 14 days of the final RCP visit and the procedure was done at the final RCP visit.
- Section 6.2.3 (Confirmation of Myasthenia Gravis Antibody Status): Clarification was provided regarding procedures for measurement of AChR and MuSK antibodies in screening.
- Section 6.3.1 (Discontinuation of Treatment): International normalized ratio cut-off for discontinuation criteria for liver abnormalities was removed.

- Section 7.2.1 (Oral Prednisone Taper): It was specified that prednisolone can be used as an alternative to prednisone at the same dose. Allowance of prednisone 10 mg every other day as an alternative to prednisone 5 mg daily was added.
- Section 7.2.2 (Rescue Medications): Information on the statistical treatment of rescue therapy was removed and will be included in the SAP.
- Section 9.4 (Methods for Statistical Analysis): Information on the statistical treatment of subjects who use corticosteroids used above the baseline dose was removed and will be included in the SAP.
- Some minor changes were made to improve wording.

### 13.9 Version 2.0

- Title page: The EudraCT number was added.
- Section 2.1.4 (Risk Assessment for Inebilizumab): Additional information was added based on an update to the IB.
- Section 2.1.5 (Anticipated Study Benefits and Risks): This section was newly added.
- Section 3.2.2 (Secondary Endpoints): Change in Patient Global Impression of Change at the end of the RCP was added as a secondary endpoint, and a description was added in Section 6.2.5.4.
- Section 3.2.2 (Secondary Endpoints), Section 3.3.2 (Exploratory Endpoints): [REDACTED]  
[REDACTED]  
[REDACTED].
- Section 4.1 (Study Design): Clarification was added for why the QMG was used instead of the MG-ADL to quantify baseline disease severity for purposes of stratification of randomization.
- Section 4.1 (Study Design), Section 4.3 (Rationale for Study Population), Section 5.1 (Inclusion Criteria): Protocol was altered to require use of immunosuppression to enter the study. Section 4.3 (Rationale for Study Population); Section 5.2 (Exclusion Criteria), #13, Section 7.2.1 (Oral Prednisone Taper): The maximum allowed dose of prednisone at study entry was changed from 60 mg daily or 80 mg every other day to 40 mg daily or 80 mg every other day.
- Section 5.1 (Inclusion Criteria), #1: Clarification was added for Japan subjects < 20 years old requiring consent of a parent or other legally authorized representative, as the current adult age in Japan is 20.
- Section 5.1 (Inclusion Criteria), #6: The minimum QMG score for enrollment was decreased from 12 to 11.
- Section 5.1 (Inclusion Criteria), #9: The laboratory value for the postmenopausal range for FSH was added.
- Section 5.2 (Exclusion Criteria): The exclusion criterion for thymoma was changed to allow enrollment of those with benign thymoma that was resected > 1 years prior to screening. Malignant thymoma was allowed if resected > 5 years prior to screening with no evidence of active disease and no therapy received over the previous 5 years.
- Section 5.2 (Exclusion Criteria): Exclusion Criterion #22d was updated from < one-half the lower limit of normal to < 40 cells/ $\mu$ L to provide the actual number.

- Section 5.2 (Exclusion Criteria): As a prohibited medication, methotrexate was changed from requiring no washout to requiring a 4-week washout before Day 1.
- Section 6.1.2 (Randomized Controlled Period): [REDACTED] was removed from the Day 57, Day 85, Day 225, and Day 267 timepoints in Table 3 and the Day 57 and Day 85 timepoints in Table 4. A Day 29 timepoint for [REDACTED] [REDACTED]
- Section 6.1.2.1 (Unscheduled Visit), Tables and 4: A description of procedures for an Unscheduled Visit was added.
- Section 6.1.3 (Open-label Period): The requirement to taper corticosteroids and non-steroidal immunosuppressants during the OLP was removed. Tapering of non-steroidal immunosuppressants was recommended per standard of care. Further tapering of corticosteroids was left to the discretion of the Investigator.
- Section 6.1.3 (Open-label Period): The duration of the OLP was increased from 12 to 18 months to allow a longer period of observation after the last dose of inebilizumab is given. The timing of visit was updated to make the intervals between visits consistent.
- Section 6.1.3 (Open-label Period), Table 5: C-SSRS testing was added to the OLP visits.
- Section 6.2.5 (Efficacy Assessments) and Section 6.2.6 (Safety Assessments): The location of where to record data of various efficacy assessments was added (ePRO system vs eCRF).
- Section 6.2.5.1 (Role of the Independent Rater): It was clarified that the independent rater performing the physical examination portion of the MGC should be physician, physician-assistant, nurse practitioner, physical therapist, or other healthcare provider who is experienced with neurological examination. It was clarified that the QMG can be performed by any independent rater who is experienced in performing the QMG and has completed the protocol training on QMG performance.
- Section 6.2.5.1 (Role of the Independent Rater), Section 6.2.5.2 (Myasthenia Gravis Activities of Daily Living): The MG-ADL was changed from the data being entered directly by the subject to being entered by a member of the site staff based on questions answered by the subject. This change was made to make the instrument used in the way that it was validated.
- Section 6.2.5.4 (Patient Global Impression of Change), Tables 3, 4, and 5: A description of the PGIC was added.

- 
- Section 6.3.1 (Discontinuation of Treatment): A discontinuation criterion was added: Platelet count  $< 50 \times 10^3/\mu\text{L}$  that does not improve to  $\geq 50 \times 10^3/\mu\text{L}$  within 14 days as agreed upon following consultation with the medical monitor.
  - Section 6.3.1 (Discontinuation of Treatment): A discontinuation criterion was added: use of prednisone  $> 10 \text{ mg/day}$  for more than 8 consecutive weeks in the OLP.
  - Section 6.3.1 (Discontinuation of Treatment): A discontinuation criterion was added: unblinding of the treatment assignment while the subject is in the RCP.

- Section 6.3.1 (Discontinuation of Treatment), Section 6.3.2 (Withdrawal from Study): The duration of follow-up after discontinuation of IP in the OLP was changed from 6 to 12 months and “until OLP Day 547” was added.
- Section 6.3.2 (Withdrawal from Study): It was clarified that subjects who discontinue IP but remain in the study should continue to have all study-related assessments except those directly related to dosing and OLP subjects should remain in the study until 12 months after last dose of IP or until OLP Day 547.
- Section 6.6 (Data Monitoring Committee): It was clarified that the DMC will evaluate study data for monitoring safety of the study.
- Section 7.2.1 (Oral Prednisone Taper): The corticosteroid taper was adjusted to make the taper slower for those entering at higher baseline prednisone doses. The corticosteroid taper in the OLP was changed from being mandatory to optional.
- Section 7.2.2 (Rescue Medications): Clarification was added regarding when rescue therapy can be used. High-dose corticosteroids were removed as an option for rescue therapy. The following statement was deleted: “Rescue medications will be considered standard of care and will not be provided or reimbursed by the Sponsor” and replaced by “Rescue therapy is considered standard of care treatment; information about Sponsor coverage of out-of-pocket costs incurred by subjects treated with rescue therapy will be included in the site contract.”
- Section 7.3.2 (Randomization Strategy and Procedure): Stratification criteria were changed to align with changes to inclusion criteria of QMG score and requirement of immunosuppression.
- Section 7.3.3 (Extent and Maintenance of Blinding): Language was added to clarify that B-cell counts and [REDACTED] after the OLP Day 15 visit will not be considered unblinding.
- Section 8.1 (Safety Assessment Definitions): Clarification was added regarding the definition of Inpatient Hospitalization for SAE purposes.
- Section 9.4 (Methods for Statistical Analysis): Additional detail on estimands and intercurrent events was added.
- Section 13 (Protocol Changes): Section 13.1 Version 2.0 was added and subsequent sections were renumbered.

## **15 APPENDICES**

## 15.1 Appendix 1 Guidance for Anaphylaxis Diagnosis

The National Institute of Allergy and Infectious Disease and Food and Allergy Anaphylaxis Network define anaphylaxis as a serious allergic reaction that is rapid in onset and may cause death. They recognize 3 categories of anaphylaxis, with criteria designated to capture from 80% of cases (Category 1) to > 95% of all cases of anaphylaxis (for all 3 categories). Their clinical criteria for diagnosing anaphylaxis are:

1. Acute onset of an illness (minutes to several hours) with involvement of the skin, mucosal tissue, or both (eg, generalized hives, pruritus or flushing, swollen lips-tongue-uvula)  
  
AND AT LEAST 1 OF THE FOLLOWING
  - a. Respiratory compromise (eg, dyspnea, wheeze-bronchospasm, stridor, reduced peak expiratory flow (PEF), hypoxemia)
  - b. Reduced blood pressure (BP) or associated symptoms of end-organ dysfunction (eg, hypotonia [collapse], syncope, incontinence)
2. 2 or more of the following that occur rapidly after exposure to a likely allergen for that subject (minutes to several hours):
  - a. Involvement of the skin-mucosal tissue (eg, generalized hives, itch-flush, swollen lips-tongue-uvula)
  - b. Respiratory compromise (eg, dyspnea, wheeze-bronchospasm, stridor, reduced PEF, hypoxemia)
  - c. Reduced BP or associated symptoms (eg, hypotonia [collapse], syncope, incontinence)
  - d. Persistent gastrointestinal symptoms (eg, crampy abdominal pain, vomiting)
3. Reduced BP after exposure to known allergen for that subject (minutes to several hours):
  - a. Infants and children: low systolic BP (age specific) or > 30% decrease in systolic BP
  - b. Adults: systolic BP of < 90 mmHg or > 30% decrease from that person's baseline.

## **15.2 Appendix 2 Actions Required in Cases of Increases in Liver Biochemistry and Evaluation of Hy's Law**

### **Introduction**

This Appendix describes the process to be followed in order to identify and appropriately report cases of Hy's Law (HL). It is not intended to be a comprehensive guide to the management of elevated liver biochemistries.

During the course of the study, the Investigator will remain vigilant for increases in liver biochemistry. The Investigator is responsible for determining whether a subject meets Potential Hy's Law (PHL) criteria at any point during the study.

The Investigator participates, together with the Sponsor's clinical project representatives, in review and assessment of cases meeting PHL criteria to agree whether HL criteria are met. HL criteria are met if there is no alternative explanation for the elevations in liver biochemistry other than Drug-Induced Liver Injury (DILI) caused by the IP.

The Investigator is responsible for recording data pertaining to PHL/HL cases and for reporting adverse events (AEs) and serious adverse events (SAEs) according to the outcome of the review and assessment in line with standard safety reporting processes.

### **Definitions**

#### Potential Hy's Law

Aspartate aminotransferase (AST) or Alanine aminotransferase (ALT)  $\geq 3 \times$  upper limit of normal (ULN) together with total bilirubin (TBL)  $\geq 2 \times$  ULN at any point during the study following the start of IP, irrespective of an increase in alkaline phosphatase (ALP).

#### Hy's Law

AST or ALT  $\geq 3 \times$  ULN together with TBL  $\geq 2 \times$  ULN, where no other reason, other than the IP, can be found to explain the combination of increases; eg, elevated ALP indicating cholestasis, viral hepatitis, another drug.

For PHL and HL, the elevation in transaminases must precede or be coincident with (ie, on the same day) the elevation in TBL, but there is no specified timeframe within which the elevations in transaminases and TBL must occur.

### **Identification of Potential Hy's Law Cases**

In order to identify cases of PHL, it is important to perform a comprehensive review of laboratory data for any subject who meets any of the following identification criteria in isolation or in combination:

- ALT  $\geq 3 \times$  ULN
- AST  $\geq 3 \times$  ULN
- TBL  $\geq 2 \times$  ULN

The Investigator will, without delay, review each new laboratory report and if the identification criteria are met will:

- Notify the Sponsor study representative.
- Determine whether the subject meets PHL criteria by reviewing laboratory reports from all previous visits.
- Promptly enter the laboratory data into the laboratory eCRF.

### **Follow-up**

#### **Potential Hy's Law Criteria Are Not Met**

If the subject does not meet PHL criteria, the Investigator will:

- Inform the Sponsor representative that the subject has not met PHL criteria.
- Perform follow-up on subsequent laboratory results according to the guidance provided in the Clinical Study Protocol.

#### **Potential Hy's Law Criteria Are Met**

If the subject does meet PHL criteria, the Investigator will notify the Sponsor study representative who will then inform the central study team. The medical monitor contacts the Investigator to provide guidance, discuss and agree on an approach for the study subject's follow-up and the continuous review of data. Subsequent to this contact, the Investigator will:

- Monitor the subject until liver biochemistry parameters and appropriate clinical symptoms and signs return to normal or baseline levels, or as long as medically indicated.
- Investigate the etiology of the event and perform diagnostic investigations as discussed with the Study Physician.
- If at any time (in consultation with the medical monitor) the PHL case meets serious criteria, report it as a SAE using standard reporting procedures.

### **Review and Assessment of Potential Hy's Law Cases**

The instructions in this section should be followed for all cases where PHL criteria are met.

No later than 3 weeks after the biochemistry abnormality was initially detected, the medical monitor will contact the Investigator in order to review available data and agree on whether there is an alternative explanation for meeting PHL criteria other than DILI caused by the IP. The medical monitor and safety physician will also be involved in this review together with other subject matter experts as appropriate.

According to the outcome of the review and assessment, the Investigator will follow the instructions below.

If there is an agreed alternative explanation for the ALT or AST and TBL elevations, a determination of whether the alternative explanation is an AE will be made and subsequently whether the AE meets the criteria for a SAE:

If the alternative explanation is not an AE, record the alternative explanation on the appropriate eCRF.

If the alternative explanation is an AE/SAE, record the AE/SAE in the eCRF accordingly and follow the Sponsor standard processes.

If it is agreed that there is no explanation that would explain the ALT or AST and TBL elevations other than the IP:

Report a SAE (report term “Hy’s Law”) according to Sponsor standard processes.

- The “Medically Important” serious criterion should be used if no other serious criteria apply
- As there is no alternative explanation for the HL case, a causality assessment of “related” should be assigned

If there is an unavoidable delay of over 3 weeks, in obtaining the information necessary to assess whether or not the case meets the criteria for HL, then it is assumed that there is no alternative explanation until such time as an informed decision can be made:

Report a SAE (report term “Potential Hy’s Law”) applying serious criteria and causality assessment as per above.

Continue follow-up and review according to agreed plan. Once the necessary supplementary information is obtained, repeat the review and assessment to determine whether HL criteria are met. Update the SAE report according to the outcome of the review.

FDA Guidance for Industry (issued July 2009) “Drug-induced liver injury: premarketing clinical evaluation”:

<https://www.fda.gov/downloads/Drugs/GuidanceComplianceRegulatoryInformation/Guidances/UCM174090.pdf>

## 15.4 Appendix 4 Study-Specified Opportunistic Infections that Meet Exclusion Criteria and Require Discontinuation of Investigational Product

Definite a,b Opportunistic Infection	Probable c Opportunistic Infection
Pneumocystis jirovecii	Paracoccidioides infections
BK virus disease including polyomavirus-associated nephropathy	Penicillium marneffei (Talaromyces)
Cytomegalovirus disease	Sporothrix schenckii
Posttransplant lymphoproliferative disorder (EBV)	Cryptosporidium species (chronic disease only)
Progressive multifocal leukoencephalopathy	Microsporidiosis
Bartonellosis (disseminated disease only)	Leishmaniasis (visceral only)
Blastomycosis	Trypanosoma cruzi infection (Chagas's disease) (disseminated disease only)
Toxoplasmosis	Campylobacteriosis (invasive disease only)
Coccidioidomycosis	Shigellosis (invasive disease only)
Histoplasmosis	Vibriosis (invasive disease due to Vibrio vulnificus )
Aspergillosis (invasive disease only)	HCV progression
Candidiasis (invasive disease or pharyngeal)	
Cryptococcosis	
Other invasive fungi: Mucormycosis (zygomycosis) (Rhizopus, Mucor and Lichtheimia), Scedosporium/Pseudallescheria boydii , Fusarium )	
Legionellosis	
Listeria monocytogenes (invasive disease only)	
Tuberculosis	
Nocardiosis	
Non-tuberculous mycobacterium disease	
Salmonellosis (invasive disease only)	
HBV reactivation	
Herpes simplex (invasive disease only)	
Herpes zoster (any form)	
Strongyloides (hyperinfection syndrome and disseminated forms only)	

EBV = Epstein-Barr virus; HBV = hepatitis B virus; HCV = hepatitis C virus.

- a Generally does not occur in the absence of immunosuppression and whose presence suggests a severe alteration in host immunity.
- b Can occur in subjects without recognized forms of immunosuppression, but whose presence indicates a potential or likely alteration in host immunity.
- c Published data is currently lacking, but expert opinion believes that risk is likely elevated in the setting of biologic therapy.

Source: Winthrop KL, Novosad SA, Baddley JW, Calabrese L, Chiller T, Polgreen P, et al. Opportunistic infections and biologic therapies in immune-mediated inflammatory diseases: consensus recommendations for infection reporting during clinical trials and postmarketing surveillance. Ann Rheum Dis. 2015;74(12):2107-16.

Additional infections may be considered to be exclusionary and to require discontinuation of IP according to the judgment of the Investigator. Investigators can also exercise discretion in recording opportunistic infections as AESIs that are not specified in Appendix 4.

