23. Any of the following laboratory abnormalities at screening (one repeat test may be conducted to confirm results prior to randomization within the same screening period):
  - a. Elevated liver enzymes (aspartate aminotransferase [AST] or alanine aminotransferase [ALT]  $> 2.5 \times$  upper limit of normal [ULN])
  - b. Total bilirubin  $> 1.5 \times$  ULN (unless due to Gilbert's syndrome)
  - c. Estimated glomerular filtration rate  $< 45$  mL/min/1.73 m^2
  - d. CD19+ B-cell count  $< 40$  cells/ $\mu$ L
  - e. Absolute neutrophil count  $< 1.2 \times 10^3$  cells/ $\mu$ L
  - f. Platelet count  $< 75,000/\mu$ L (or  $< 75 \times 10^9/L$ )
  - g. Hemoglobin  $< 8.0$  g/dL
  - h. Total Ig  $< 600$  mg/dL
24. Positive test for chronic hepatitis B infection at screening, defined as either 1) positive hepatitis B surface antigen (HBsAg) or 2) a positive hepatitis B core antibody (anti-HBc) PLUS negative hepatitis B surface antibody (anti-HBs).  
Note: Subjects with a positive anti-HBs only, or a positive anti-HBc plus positive anti-HBs and negative HBsAg, are eligible to enroll.
25. History of untreated hepatitis C infection, or positive antibody test for hepatitis C virus (HCV) unless the subject is considered to be cured following antiviral therapy and has an HCV viral load below the limit of detection  $\geq 24$  weeks after completion of treatment at site or central lab.
26. Positive HIV test.
27. Blood transfusion within 4 weeks prior to screening or during the screening period.
28. Inability to read.
29. History of active or latent tuberculosis (TB), or a positive QuantiFERON®-TB Gold test at screening, unless treatment for TB was completed per local guidelines. Subjects with latent TB or a positive QuantiFERON®-TB Gold test who are actively on anti-TB treatment can enroll if they have completed  $\geq 1$  month of anti-TB treatment and intend to complete the full course of anti-TB treatment. Subjects with an indeterminate QuantiFERON®-TB Gold test result can enroll if a repeat QuantiFERON®-TB Gold is negative or a tuberculin skin test is negative.
30. Hospitalization for any reason  $< 30$  days prior to randomization.
31. Current or recent MG deterioration that has not returned to baseline/resolved within  $\geq 30$  days prior to randomization.

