## 6.3 Discontinuation or Withdrawal

### 6.3.1 Discontinuation of Treatment

The IP must be discontinued in the following circumstances:

1. If the Investigator determines that continuing treatment would result in a significant safety risk to the subject, and consult with the Sponsor medical director.
2. After randomization, if identified that a subject has not met the eligibility criteria and there is a potential safety risk, and consult with the Sponsor medical director.
3. Any life-threatening (Grade 4) clinical event related to the IP, and consult with the Sponsor medical monitor.
4. An AE that, in the opinion of the Investigator or the Sponsor, contraindicates further dosing.
5. Subject becomes pregnant.
6. Any of the following liver function abnormalities:
  - a. ALT or AST  $\geq 8 \times$  ULN
  - b. ALT or AST  $\geq 5 \times$  ULN for more than 2 weeks without alternative explanation
  - c. ALT or AST  $\geq 3 \times$  ULN and total bilirubin  $\geq 2 \times$  ULN without alternative explanation
7. ALT or AST  $\geq 3 \times$  ULN with the appearance of fatigue, nausea, vomiting, right upper quadrant pain or tenderness, fever, rash, and/or eosinophilia ( $\geq 5\%$ ) without alternative explanation.
8. Neutrophil count  $< 1.0 \times 10^3/\mu\text{L}$  (Grade 3 or 4 neutropenia) that does not improve to  $\geq 1.0 \times 10^3/\mu\text{L}$  within 14 days as agreed upon consultation with the medical monitor.
9. Platelet count  $< 50 \times 10^3/\mu\text{L}$  (Grade 3 or 4 thrombocytopenia) that does not improve to  $\geq 50 \times 10^3/\mu\text{L}$  within 14 days as agreed upon consultation with the medical monitor.
10. Receipt of a prohibited medication that is considered to be an unacceptable risk following consultation with the medical monitor (see [Section 7.5.2](#)).
11. Use of corticosteroid (prednisone  $> 10$  mg/day or equivalent) for more than 8 consecutive weeks in the OLP.
12. Unblinding of the treatment assignment while the subject is in the RCP.

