#### 7.1.1.4 Dosing and Administration

Prior to the IP infusion, Investigators must determine whether there is a clinically significant infection. In case of infection, the IP infusion will be delayed until the infection resolves.

Premedication with a corticosteroid (eg, methylprednisolone 100 mg IV or equivalent; equivalent methylprednisolone dose should be calculated using [Table 9](#) below) will be administered

approximately 30-60 minutes prior to each inebilizumab infusion, and an antihistamine (eg, diphenhydramine 25-50 mg orally or equivalent) and an anti-pyretic (eg, acetaminophen 500-650 mg orally or equivalent) will be administered approximately 30-60 minutes prior to each IP infusion. Sites should use local supplies of these premedications.

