#### Collection of Lactation Information

- Investigator will collect lactation information on any participant who breastfeeds while taking IP through 6 months after the last dose of IP.
- Information will be recorded on the Lactation Notification Form (see below) and submitted to the Sponsor's Global Patient Safety immediately and no later than 24 hours of the Investigator's awareness of the event.

- Study treatment will be discontinued if a participant breastfeeds during the study as described in the exclusion criteria (see [Section 5.2](#)).
- With the participant's signed consent for release of parent and infant health information, the Investigator will collect mother and infant health information and complete the lactation questionnaire on any participant who breastfeeds while taking IP through 6 months after the last dose of IP.

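### Appendix 4 requires stopping IP for listed opportunistic infections, but the mandatory stopping list omits them and the dosing section only delays the infusion

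*Protocol*

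**What the plan says.** The heading of Protocol Appendix 4 reads "Study-Specified Opportunistic Infections that Meet Exclusion Criteria and Require Discontinuation of Investigational Product". The table below it includes, among others, herpes zoster in any form, tuberculosis and progressive multifocal leukoencephalopathy. The closing text adds: "Additional infections may be considered to be exclusionary and to require discontinuation of IP according to the judgment of the Investigator".

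Protocol Section 6.3.1 opens with "The IP must be discontinued in the following circumstances" and gives 12 numbered items: safety risk, ineligibility with a potential safety risk, a related Grade 4 event, a contraindicating adverse event, pregnancy, two liver items, neutropenia, thrombocytopenia, prohibited medication, prolonged open-label corticosteroid use, and unblinding in the RCP. Section 2.1.5 refers to this section for the criteria for required discontinuation.

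Protocol Section 7.1.1.4 has the Investigator check for a clinically significant infection before each infusion, and then says: "In case of infection, the IP infusion will be delayed until the infection resolves".

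Protocol Section 8.5 refers to Appendix 4 for the list of opportunistic infections that count as adverse events of special interest, to be reported within 24 hours. It gives no dosing instruction. The exclusion criteria in Section 5.2 do not refer to the appendix.

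**The concern.** A site that looks for the rule on a listed infection finds three different answers. The appendix heading is categorical: stop. The section that sets out mandatory stops does not mention the event. The section used on every dosing day says to wait until the infection has resolved. The protocol states no order of precedence among them.

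Subject safety comes first. Section 2.1.4 names serious infection and PML as important potential risks of a B-cell-depleting drug, and inclusion criterion 7 has every subject entering on a corticosteroid, another immunosuppressant, or both. Consistent conduct comes second. A permanent stop sends the subject down a different path: in the RCP, no further IP but continued visits and then safety follow-up; in the open-label period, an early discontinuation visit and safety follow-up. Several reported quantities therefore depend on which section a site happened to read.

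**Working it through.** No figure in the plan is at issue, so the check sets the passages side by side, follows one case through them, and counts the dosing decisions exposed.

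**1. Is the Appendix 4 heading a rule or only a label?** The closing text leaves *additional* infections to the Investigator's judgment, both for exclusion and for discontinuation. That makes sense only if the listed infections are not left to judgment. The heading therefore reads as a rule.

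**2. Does Section 6.3.1 contain the rule?**
- Items that name an infection or cite Appendix 4: 0 of 12.
- Items that could reach a listed infection by judgment: 2 of 12. These are item 1 ("If the Investigator determines that continuing treatment would result in a significant safety risk to the subject") and item 4 ("An AE that, in the opinion of the Investigator or the Sponsor, contraindicates further dosing").
- Item 3 could reach one only if the event is Grade 4 and related to IP.

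The list is numbered without gaps and shows no redaction.

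**3. Does another section carry the rule?** Section 7.1.1.4 has no exception for Appendix 4 infections. Section 8.5 tells the site to report. Section 5.2 covers parts of the ground (for example criteria 18, 19, 24, 25 and 29) but never cites the appendix, so the heading's statement that the infections meet exclusion criteria has no matching general criterion.

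**4. One case followed through.** A subject has herpes zoster that clears before the next infusion.
- Reading Appendix 4: the infection is listed, so IP is discontinued.
- Reading Sections 8.5, 6.3.1 and 7.1.1.4: the event is reported; no item compels a stop unless the Investigator or Sponsor judges that item 1 or 4 applies; the infection has resolved, so nothing delays the infusion and it is given.

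The second course is a deviation under the appendix and compliant under the other three sections.

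**5. Where in the trial the conflict can act.** Infusion days are in Protocol Table 8. The counts below are maxima, because the open-label period is optional.
- AChR-Ab+: 3 in the RCP (Days 1, 15, 183) plus 7 open-label (Days 1, 15, 183, 365, 547, 729, 911) = 10. After the first infusion, 10 − 1 = 9 dosing decisions.
- MuSK-Ab+: 2 in the RCP (Days 1, 15) plus 7 open-label = 9. After the first infusion, 9 − 1 = 8 dosing decisions.
- For subjects from an active arm, one of the 7 open-label infusions (Day 15) is placebo.
- Before the Week 26 assessment only the Day 15 infusion remains, which is 1 decision. The AChR-Ab+ Day 183 infusion follows that visit's assessments (Section 6.1.2; Table 3 footnotes), and the MuSK-Ab+ Day 183 procedures must be finished before any open-label dose (Table 4 footnotes).
- So up to 9 − 1 = 8 (AChR-Ab+) and 8 − 1 = 7 (MuSK-Ab+) of the decisions come after the Week 26 assessment.

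**6. Which analyses are touched.** Protocol Sections 9.4.1 and 9.4.2 handle treatment discontinuation by treatment policy, and Section 6.3.1 asks subjects who stop IP to stay on the RCP visit schedule. The Week 26 data are therefore kept whichever course a site takes. The outputs that do vary by site are deviation classification (SAP 3.2), disposition (SAP 3.3.1), exposure and compliance (SAP 3.3.3), the count of treatment-emergent events leading to discontinuation of IP (SAP 3.5.1.2), and any while-on-treatment safety analysis (Protocol 9.4.7).

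**The case against.** The strongest reply is that the texts can be read together. Section 7.1.1.4 is a general pre-infusion check, Appendix 4 is a specific rule for named infections, and Section 6.3.1 does not say that its list is exclusive. A site could hold the infusion for any infection, stop IP for a listed one, and breach nothing. Section 8.5 sends the site to the appendix, where the heading is in plain view. Reporting within 24 hours also tells the Sponsor, who can then invoke item 4.

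Much of this stands. A reader might infer that sites cannot follow the protocol, or that it orders re-dosing after a listed infection. The documents support neither. A consistent reading exists, the protocol speaks of delay until resolution, and giving the next infusion afterwards is the plain implication rather than a stated instruction. What does not fall away is that items 1 and 4 are discretionary while the appendix is categorical, and that nothing tells a site the specific text overrides the general one.

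Two neighbouring points are weaker than they look. Criterion 29 admits some subjects with a tuberculosis history, for instance "unless treatment for TB was completed per local guidelines", while the appendix lists tuberculosis without qualification. But criterion 29 is itself an exclusion with exceptions, so this is a mismatch to tidy and not a clear contradiction. Section 8.4.1 says "Study treatment will be discontinued if a participant breastfeeds during the study", which Section 6.3.1 also omits. No section says to continue dosing in that case, so it shows an incomplete list and not a conflict.

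**Conclusion.** The inconsistency is real and lies in the current text. A site that follows Sections 6.3.1 and 7.1.1.4 to the letter could give a further infusion where Appendix 4 says to stop.

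Its size in subjects cannot be computed, because the documents give no expected incidence for any listed infection in this trial. A reader might infer a large effect from the inclusion of herpes zoster in any form, but the documents do not say how often it occurs, and the point does not need it to be frequent.

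A reader might also infer that the primary result is at risk through the treatment-discontinuation intercurrent event. That does not follow. Discontinuation is handled by treatment policy, and only the Day 15 infusion falls between first dose and the Week 26 assessment, so the effect on the primary and key secondary estimands is minimal. There is somewhat more room at Week 52 in the AChR-Ab+ population, because the Day 183 dose comes before it.

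The weight of the point is subject safety and consistent handling of IP at Day 183 and in the open-label period, with knock-on variation in exposure, disposition, deviation and discontinuation summaries. This rests on reading the appendix heading as binding, which its closing text supports, and on there being no precedence rule in the protocol as provided.

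**What to change.** Reconcile Protocol Sections 5.2, 6.3.1, 7.1.1.4, 8.5 and Appendix 4 so that one section holds the complete set of mandatory stopping circumstances and the others refer to it. Bring the breastfeeding stop in Section 8.4.1 into the same list. State how the delay instruction in Section 7.1.1.4 relates to the listed infections. Either point Section 5.2 to the appendix or align the heading's statement about exclusion criteria with Section 5.2, including the tuberculosis wording. Which clinical rule applies is for the sponsor's medical team; none is proposed here.

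Send sites a clarification letter without waiting for the amended text. No new data collection is needed: Section 8.2 already records the action taken for each adverse event and Section 7.4 the dose and date of each infusion. From these, the study report can show, for each Appendix 4 infection, whether dosing stopped or went on. The cost is a letter and a protocol amendment, with no added procedures for subjects.
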